1.2 BACKGROUND AND RATIONALE

1.2.1 Adrenocortical Carcinoma

Adrenocortical carcinoma (ACC) is a rare tumor with an incidence of 1.5 to 2 per million people per year¹⁻³. It has a very poor prognosis with an overall 5-year mortality rate of 75 - 90% and an average survival from the time of diagnosis of 14.5 months. Signs and symptoms due to excess hormonal secretion are seen in a large fraction of patients, further contributing to the morbidity associated with this disease.

The treatment of choice for a localized primary or recurrent tumor is surgical resection. Excisable primary tumors represent about 40% of cases at presentation; however, 60 - 80% of these patients eventually die from recurrent extensive metastases⁴. Patients with recurrent or metastatic disease are infrequently curable by surgery alone due to the propensity for intraperitoneal recurrence.

For unresectable metastatic or recurrent disease, mitotane, aminoglutethimide, metapyrone, and ketoconazole are used. Of these, mitotane is the only agent with both anti-tumor and adrenolytic effects. Aminoglutethimide, metapyrone, and ketoconazole are used to treat the symptoms of excess hormone production in patients with functional tumors. Mitotane, the most extensively studied agent, was reported to have response rates of 30-60% in older studies without standardized response criteria or the use of modern imaging technology⁵⁻⁷. Response rates of 20% or less have been noted with more modern imaging technology. These responses persist for an average of 10.5 months with no apparent impact on overall survival.

Most reports of cytotoxic therapy for ACC are anecdotal or include a small number of patients⁸⁻¹³. These studies report low response rates with the majority of responses classified as partial and

of less than one year in duration. Trials using mitotane in combination with various chemotherapeutic agents have had similar results^{12, 13}. The largest randomized trial for metastatic or locally advanced ACC conducted was recently published and showed that a regimen of etoposide, doxorubicin and cisplatin (EDP) combined with mitotane was superior to the combination of streptozocin and mitotane with a median PFS of 5.0 months vs. 2.1 months and response rate of 23.2 and 9.2% respectively¹⁴.

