3.10 POST DISCHARGE

- CBC weekly following discharge or until toxicities have resolved (less than grade 3 or baseline) and patient has recovered from nadir. This may be done through the patient's referring physician with the results faxed to [name] or her designee.
- Patients will return to clinic approximately 4-8 weeks following surgery for their 1st post-operative visit and will be followed as clinically indicated until recovery. Upon recovery from the surgical procedure, the following end of treatment evaluations will be performed:
 - Imaging studies to establish new baseline
 - Tumor markers as indicated
 - CBC, acute care, mineral and hepatic panel, CRP, Albumin, pre-albumin, ferritin, Hgb A1c if elevated pre-op.
 - Physical examination to include ECOG, weight and vital signs
 - QOL survey

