3.11 TREATMENT ASSESSMENT AND RESPONSE (FOLLOW UP PERIOD)

- Because of the nature of peritoneal imaging and because cytoreductive surgery will likely eliminate all imageable disease, response can only be measured in terms of radiographic disease-free survival. At any time point when there is evidence of progressive disease (imageable tumor nodules or increasing ascites persistent on CT scans as interpreted by the official interpretation of the imaging studies) the patients will be scored as progressive disease. In some cases this may require successive scans, but the time of

recurrence will be retrospectively defined at the point the first scan demonstrated imageable disease.

- Patients will be evaluated 3 months from the operative date (+/- 1 month) intervals for the first year; every four months for (+/- 1 month) the next year and then q 6 months (+/- 1 month) thereafter.
- The following evaluations will be performed at each visit:
 - Imaging studies
 - Physical examination to include ECOG, weight and vital signs
 - Tumor markers as indicated
 - CBC, acute care, mineral and hepatic panel, CRP, Albumin, pre-albumin, ferritin, Hgb A1c if elevated pre-op.
 - Completion of Health related Quality of Life Forms (HRQOL) – at the first follow up visit and then at each evaluation until off study.
- Patients who are unwilling or unable to return for follow up evaluation will be followed every 6 months by phone contact until off study criteria are met. The following information may be obtained:
 - Summary of treatment received since the previous contact
 - Estimation of ECOG status
 - Request for imaging studies, physical exam and laboratory reports to be sent to the PI

Note: if patient is taken off study prior to 1 year following surgery, the HRQOL will be completed at the off study evaluation if possible.

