8 STATISTICAL CONSIDERATIONS

The primary objective of this trial is to conduct a pilot study to determine if the use of debulking surgery and HIPEC in patients with intra-peritoneal spread of adrenocortical carcinoma is able to be associated with an intra-peritoneal progression free interval which may exceed that of the use of chemotherapy alone.

Data from a recently published study indicated that a 5.0 month median PFS¹⁴ may be attained in similar patients using EDP and mitotane. This will be a single arm trial with the goal of seeing if the proposed combination of HIPEC and surgery may be associated with a 10 month median PFS. Using the method of Brookmeyer and Crowley³³, the study will plan to enroll 24 fully evaluable patients over a 60 month period. Based on this method, with 24 subjects, there would be 80% power to determine if there is a median PFS of 10 months rather than 5 months, based on a one-tailed 0.10 alpha level test. In practice, Kaplan-Meier curves and appropriate confidence intervals at selected time points will be provided to help interpret the results relative to historical results.

At the rate of 6 patients per year, 24 evaluable patients could be enrolled in 5 years, allowing for a ceiling of 30 patients to account for patients who may be inevaluable.

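### Section 8's one-tailed 0.10 and 80% power hold only as a normal approximation with exact progression times; the interval scale and the benchmark's scan schedule are not stated

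*Combined protocol and SAP*

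**What the plan says.** Section 8 plans a single-arm comparison by the Brookmeyer-Crowley method, with 24 evaluable patients and a one-tailed 0.10 level, and states that "there would be 80% power to determine if there is a median PFS of 10 months rather than 5 months". It does not name the scale of the confidence interval or the number of progression-free patients that would put the lower limit above 5 months. For reporting, it says that "Kaplan-Meier curves and appropriate confidence intervals at selected time points will be provided to help interpret the results relative to historical results".

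The null value comes from one published trial: "Data from a recently published study indicated that a 5.0 month median PFS" could be reached in similar patients. Section 1.2.1 describes the same trial's regimen as "superior to the combination of streptozocin and mitotane with a median PFS of 5.0 months vs. 2.1 months". Neither place says how often those patients were assessed.

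Section 3.11 sets how progression is dated here. Its schedule reads "Patients will be evaluated 3 months from the operative date (+/- 1 month) intervals for the first year", so the first scans fall at about months 3 and 6. When successive scans are needed, the time of "recurrence will be retrospectively defined at the point the first scan demonstrated imageable disease". Progression can also be scored outside the schedule: "At any time point when there is evidence of progressive disease" is how the rule opens. Section 3.10 adds a new postoperative imaging baseline without fixing its date: "Upon recovery from the surgical procedure, the following end of treatment evaluations will be performed".

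**The concern.** The trial has no control arm, so its efficacy reading is the comparison of its own median PFS with 5.0 months. That value lies between the month-3 and month-6 scans. A patient who progresses at month 4 and is next scanned at month 6 counts as progression-free at month 5. The Kaplan-Meier value at 5 months therefore mostly reports who was clear at the first follow-up scan. Whether this biases the comparison depends on how the 5.0 months was itself dated, which the documents do not say.

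A second gap needs no assumption about the benchmark. With 24 patients the possible results are coarse, and the choice of interval scale moves the required count by one patient. If neither is stated, a reader who sees a lower limit above 5 months cannot separate treatment effect from scan timing or interval scale.

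**Working it through.** **Inputs.** From section 8: n = 24, one-tailed 0.10 (critical value 1.282), medians 5 and 10 months. From section 3.11: first follow-up scan at month 3 ± 1. Assumed: exponential times, no censoring before month 5, first scan uniform over months 2 to 4, second scan not before month 5.

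**1. The plan's own figure.** Progression-free probability at 5 months: null 0.50; alternative 2^(−5/10) = 0.707.
- Null SE = √(0.25/24) = 0.1021, so the threshold is 0.50 + 1.282 × 0.1021 = 0.631.
- Alternative SE = √(0.707 × 0.293/24) = 0.0929.
- Power = Φ((0.707 − 0.631)/0.0929) = Φ(0.82) = 79.4%.

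The stated 80% reproduces. The threshold corresponds to 24 × 0.631 = 15.1 patients, between two attainable counts.

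**2. The attainable rule with exact times.** The lower limit for the median exceeds 5 months when the estimate at 5 months lies more than 1.282 standard errors above 0.50 on the chosen scale. For 15 of 24 the estimate is 0.625, with SE √(0.625 × 0.375/24) = 0.0988.
- Plain scale: 0.125/0.0988 = 1.265, not enough. Sixteen gives 1.732.
- Log-log scale: 1.155, not enough. Sixteen gives 1.506.
- Log scale: ln(0.625/0.50)/(0.0988/0.625) = 1.411, enough.

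Binomial tails with n = 24:

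| Rule | Size (p = 0.50) | Power (p = 0.707) |
|---|---|---|
| at least 16 (plain, log-log) | 7.6% | 75.1% |
| at least 15 (log) | 15.4% | 86.5% |

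**3. What the scan grid does to the value at 5 months.** For true median m, the observed value is the average of 2^(−u/m) over u from 2 to 4, which equals m/(2 ln 2) × [2^(−2/m) − 2^(−4/m)].
- m = 2.96: 0.500
- m = 5: 0.662
- m = 10: 0.813

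A true median of about 3 months is therefore enough to show 50% progression-free at month 5.

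**4. Size by assumed benchmark schedule.** For each schedule, find the true median that gives an observed value of 0.50 at month 5, then apply step 3. Under random phase, the benchmark's last scan before month 5 is uniform over the preceding interval. Under anchored scanning, it falls at the last multiple of the interval from baseline.

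| Assumed benchmark dating | True median behind 5.0 | Observed value at 5 months here | Size, 16 of 24 | Size, 15 of 24 |
|---|---|---|---|---|
| Same grid as this trial | 2.96 | 0.500 | 7.6% | 15.4% |
| Every 2 months, random phase | 3.97 | 0.595 | 31% | 47% |
| Every 2 months, anchored (month 4) | 4.00 | 0.598 | 32% | 48% |
| No scan lag (upper bound) | 5.00 | 0.662 | 57% | 73% |
| Every 4 months, random phase | 2.84 | 0.485 | 5.7% | 12% |
| Every 4 months, anchored (month 4) | 4.00 | 0.598 | 32% | 48% |
| Every 5 months, random phase | 2.17 | 0.391 | 0.6% | 1.7% |
| Every 5 months, anchored (month 5) | 5.00 | 0.662 | 57% | 73% |

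At 2 months the two phase assumptions agree. At 4 and 5 months they point in opposite directions.

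**5. Power at section 8's own alternative, 16 of 24.**
- True median 10 months: observed value 0.813, power 98%.
- Ten months as an observed median on this grid (decided by a scan at months 8 to 10): true median about 9.0, observed value 0.794, power 96%.

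**6. What shrinks the inflation.** For the 2-monthly random-phase benchmark, 31% falls to 24% if 20% of events are dated exactly in both trials. It falls to 22% if the ± 1 month applies to each gap, which puts a second scan before month 5 in 12.5% of patients. With 10% censored by month 5, it is 32%.

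**The case against.** The strongest reply is that the benchmark is presumably scan-dated too. Brookmeyer-Crowley is nonparametric: if 5.0 months is an observed median on this trial's grid, the null value at month 5 is 0.50 and the size is exactly what it would be with exact times. That stands. Scan dating alone does not break the size; an unstated difference in schedules can.

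It can also be said that section 8 calls this a pilot, sets no formal rejection rule, and that planning on a normal approximation is common. Those points lower the severity. They do not remove the gap, because section 8 quotes both error rates alongside its sample size and says the intervals will be read against historical results.

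Four stronger readings are tempting, and the documents do not support them:
- A reader might infer that the false-positive rate is 57%. That requires a benchmark with no scan lag, so it is an upper bound and not an estimate.
- A reader might infer that a benchmark scanned less often makes the comparison conservative. The result depends on where its scans fall: 4-monthly scanning gives 5.7% at random phase and 32% when anchored.
- A reader might infer that scan dating leaves the trial underpowered. At section 8's 10-month alternative, power on this grid is 96% to 98%.
- A reader might call the 80% an arithmetic error. It reproduces; it is an approximation that no attainable count delivers.

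**Conclusion.** The concern holds in two limited parts.

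First, with exact times and no early censoring, the nominal 10% and 80% are really 7.6% and 75% on the plain scale, or 15.4% and 86.5% on the log scale. Section 8 does not say which applies. This part rests on section 8's own inputs and exponential times.

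Second, the comparison with 5.0 months rests mostly on the first follow-up scan, and its validity depends on a benchmark schedule that the documents omit. The size is unchanged on the same grid. The comparison leans towards benefit if the benchmark was assessed clearly more often, as at 2 months (about 31%). For wider intervals no general direction can be given.

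The rates assume exponential times, no early censoring and a first scan spread evenly over months 2 to 4. Deaths and unscheduled scans reduce the inflation. That section 8 assumes exact times is inferred: the 80% reproduces that way, and no allowance for scan dating is described. This should be corrected, but it does not invalidate the design. Confidence is medium, because the size of the second part is a range.

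**What to change.** In section 8:

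1. Name the confidence-interval scale and the resulting count of 24, and restate the figures. For the plain scale with exact times: at least 16 of 24, size 7.6%, power 75%.
2. State that PFS is scan-dated under section 3.11. Give the assessment schedule behind the 5.0 months or the assumption made about it. Show the size over a range of schedules, saying whether scans are taken as anchored or at random phase, and compute power at the plan's own 10-month alternative.
3. Keep the scan-dated Kaplan-Meier analysis as primary. Record the dates of the last clear and first positive scans, and add a prespecified interval-censored median as a sensitivity analysis that does not decide the claim.

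Section 6.2.2 leaves evaluations done only for clinical indications out of the database, so one explicit line is needed to capture unscheduled scan dates.

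The cost is some wording, one simulation, two dates per patient and one standard fit; visits stay as they are. There are two downsides. On the plain scale the stated power becomes slightly less favourable. The interval-censored median is also conservative against a scan-dated benchmark: on the same grid, a benchmark of 5.0 corresponds to a true median of about 3 months, yet the estimate would still be set against 5. That is why it should inform the reading and not decide it.

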9 HUMAN SUBJECTS PROTECTION

9.1 RATIONAL FOR SUBJECT SELECTION

The investigational nature and objectives of this trial, the procedure and the treatments involved, the attendant risks and discomforts, potential benefits and potential alternative therapies will be carefully explained to the patient in the clinic setting and in the hospital prior to treatment and prior to obtaining a signed Informed Consent. This is particularly important for this study because of the relatively unique nature by which the treatment is given. That is to say, the patients must subject themselves to a major operative procedure with the attendant risks and complications associated with it in order to receive treatment without any assurance of benefit from the treatment.

9.2 PARTICIPATION OF CHILDREN

The surgical regimen used in this protocol is a major procedure which entails serious discomforts and hazards for the patient, such that fatal complications are possible. It is therefore only appropriate to carry out this experimental procedure in the context of life threatening adrenocortical carcinoma. Since the efficacy of this experimental procedure is unknown, it does not seem reasonable to expose children to this risk without further evidence of benefit. Should results of this study indicate efficacy in treating adrenocortical carcinoma, which is not responsive to other standard forms of therapy, future research can be conducted in the pediatric population to evaluate potential benefit in that patient population.

9.3 PARTICIPATION OF SUBJECTS UNABLE TO GIVE CONSENT

Adults unable to give consent are excluded from enrolling in the protocol. However, re-consent may be necessary and there is a possibility, though unlikely, that subjects could become decisionally impaired. For this reason and because there is a prospect of direct benefit from research participation (section 9.5), all subjects will be offered the opportunity to fill in their wishes for research and care, and assign a substitute decision maker on the “NIH Advance Directive for Health Care and Medical Research Participation” form so that another person can make decisions about their medical care in the event that they become incapacitated or cognitively impaired during the course of the study. Note: The PI or AI will contact the NIH Ability to Consent Assessment Team for evaluation. For those subjects that become incapacitated and do not have pre-determined substitute decision maker, the procedures described in MAS Policy 87-4 for appointing a surrogate decision maker for adult subjects who are (a) decisionally impaired, and (b) who do not have a legal guardian or durable power of attorney, will be followed.

9.4 EVALUATION BENEFITS AND RISKS/DISCOMFORTS

The potential benefit to patients undergoing this therapy would be palliation in terms of preventing or delaying intra-abdominal tumor progression and metastases elsewhere which can be a devastating and painful source of symptoms and cause for demise. In addition, significant tumor response may extend progression free and overall survival. The risks for this protocol include the risks associated with any abdominal surgery. This includes postoperative bleeding, intra-abdominal infection, enterocutaneous fistulas, anesthetic mishap and perioperative death. In addition, the toxicities of chemotherapy place the patients under risk. A combination of surgery and chemotherapy may decrease healing at a time when healing of abdominal wounds and bowel anastomosis is essential for recovery. All attempts will be made to avoid

enterotomies or a bowel resection where feasible. In the case of intra-abdominal catastrophe after surgery, patients may require reoperation.

9.5 RISKS/BENEFIT ANALYSIS

Patients with peritoneal carcinomatosis suffer with recurrent bowel obstructions, nausea, vomiting, crampy abdominal pain and incapacitating ascites. This clinical scenario justifies aggressive treatment strategies as a means of palliation and survival benefit. In Phase I and II trials we have seen long-term remissions after HIPEC in patients who were otherwise terminal with no other therapeutic options available.

The potential benefit is great for these patients if a regional response is obtained.

There is a direct benefit to patients to stay on study during the follow up period because we follow them for disease recurrence. If or when we identify disease recurrence, we are often able to facilitate treatment, either on an NCI investigator protocol, or by referring to a colleague that treats the same disease process.

Therefore, this protocol involves greater than minimal risk, but presents the prospect of direct benefit to individual subjects.

9.6 CONSENT PROCESS AND DOCUMENTATION

All patients are thoroughly screened prior to initial consultation at the NIH. This usually involves a telephone conversation between the patient and a physician or nurse associate investigator. During the initial consultation the patient, along with family members, is presented a forthright and detailed overview of the treatment option available to them at the NIH. The experimental nature of the treatment, its theoretical advantages and disadvantages, and an overview of the operative procedure and anticipated convalescence are presented. The fact that the patient may undergo an operative procedure in order to receive therapy without any assurance of benefit, the aggressive nature of the treatment, and the likelihood of serious or potentially life-threatening complications are presented. The Informed Consent document is given to the patient and they are asked to review it, make notes and follow-up with a phone call to the physician or nurse investigator to have any additional questions answered prior to considering treatment on protocol.

When the patient is admitted to the Clinical Center for treatment, an associate physician investigator responsible for the care of the patient presents the previously described information in detail. The research nurse or Principal Investigator, or designee is responsible for obtaining consent from the patient upon admission. The patient is reassured that participation on the trial is entirely voluntary and that they can withdraw or decide against treatment at any time without adverse consequences. In fact, the investigators assure the patient that if alternate therapies are preferred that we will do all that we can to facilitate obtaining consultation and treatment from the appropriate medical center. The signed consent will be verified by the physician responsible for the care of the patient. The patient is asked to participate in completing the self-administered questionnaires measuring health related quality of life during this study. They are assured that their eligibility to participate in the perfusion portion of this study is not dependent upon their willingness to complete the quality of life questionnaires.

9.6.1 Re-consent via telephone

The informed consent document will be sent to the subject. An explanation of the study will be provided over the telephone after the subject has had the opportunity to read the consent form. The subject will sign and date the informed consent. A witness to the subject's signature will sign and date the consent.

The original informed consent document will be sent back to the consenting investigator who will sign and date the consent form with the date the consent was obtained via telephone.

A fully executed copy will be returned via mail for the subject's records.

The informed consent process will be documented on a progress note by the consenting investigator and a copy of the informed consent document and note will be kept in the subject's research record.

